7.1.5.4 Critical Procedures Based on Trial Objectives: Timing of Procedure

For this trial, the blood sample collection for MK-5160 and glargine is the critical procedure as is the glucose clamp procedure.

At any post-dose timepoint, the blood sample for MK-5160 needs to be collected as close to the exact timepoint as possible. All other procedures should be completed as close to the prescribed/scheduled time as possible. Trial procedures can be performed prior or after the prescribed/scheduled time.

The order of priority can be changed during the trial with joint agreement of the investigator and the Sponsor Clinical Director.

Any nonscheduled procedures required for urgent evaluation of safety concerns take precedence over all routine scheduled procedures.

The following variance in procedure collection times will be permitted.

- PK Collection as outlined in [Table 6](#) below

Table 6 PK (Blood) Collection Windows

PK collection relative to dose	PK Collection Window
hr	+/- 5 min
> 1 hr	+/- 15 min
24 hr (daily)	+/- 30 min
> 48 hr after last dose	+/- 2 hours

- Non-clamp day standard safety evaluations: (vital signs & ECG) - +/- 3 hrs (predose); (laboratory safety tests & physical exam) - +/- 6 hrs
- Clamp day standard safety evaluations (vital signs, ECG, laboratory safety tests, physical exam): +/- 30 mins
- Pharmacodynamic or other protocol specific measurements, or modification to any of the above windows:
 - NEFA, glycerol, glucagon, triglycerides, C-peptide, and endogenous insulin: +/- 30 minutes
 - ADA/AIA: +/- 6 hours
- Study drug administration: +/- 30 mins

7.1.5.5 Trial Design/Dosing/Procedures Modifications Permitted within Protocol Parameters

This is a Phase I assessment of MK-5160 in humans, and the pharmacokinetic, pharmacodynamic and safety profiles of the compound is still being elucidated. This protocol is written with some flexibility to accommodate the inherent dynamic nature of Phase I clinical trials. Modifications to the dose, dosing regimen and/or clinical or laboratory procedures currently outlined below may be required to achieve the scientific goals of the trial objectives and/or to ensure appropriate safety monitoring of the trial subjects.

As such, some alterations from the currently outlined dose and/or dosing regimen may be permitted based on newly available data, but the maximum daily dose may not exceed those currently outlined in the protocol.

- Repeat of or decrease in the dose of the trial drug administered in any given period/panel
- Interchange of doses between panels
- Entire period(s) or panel(s) may be omitted
- Decrease in the duration of trial drug administration (e.g., number of days)
- Remove a planned pharmacokinetic pause if agreed by Sponsor and investigator if no further increases in total daily dose
- Addition of pharmacokinetic pause
- Addition of operational pause
- Decrease in the target glycemic level to be maintained during glucose infusion/clamp procedure
- Decrease in number of PK sampling timepoints
- Modification of the PK/PD sample processing and shipping details based on newly available data
- Modification of urine sample collection to another panel or period

The pharmacokinetic/pharmacodynamic sampling scheme currently outlined in the protocol may be modified during the trial based on newly available pharmacokinetic or pharmacodynamic data (e.g., to obtain data closer to the time of peak plasma concentrations). If indicated, these collected samples may also be assayed in an exploratory manner for metabolites and/or additional pharmacodynamic markers.

Up to additional 50 mL (NOTE: Never more than 50 mL) of blood may be drawn for safety, pharmacokinetic, and/or pharmacodynamic analyses. The total blood volume withdrawn from any single subject will not exceed the maximum allowable volume during his/her participation in the entire trial (Section 12.3).

The timing of procedures for assessment of safety procedures (e.g., vital signs, ECG, safety laboratory tests, etc.) currently outlined in the protocol may be modified during the trial based on newly available safety, tolerability, pharmacokinetic or pharmacodynamic data (e.g., to obtain data closer to the time of peak plasma concentrations). Additional laboratory safety tests may be added to blood samples previously drawn to obtain additional safety information (e.g., adding creatinine kinase to serum chemistry panel that was already drawn). These changes will not increase the number of trial procedures for a given subject during his/her participation in the entire trial.

It is understood that the current trial may employ some or none of the alterations described above. Any alteration made to this protocol to meet the trial objectives must be detailed by the Sponsor in a letter to the Trial File and forwarded to the investigator for retention. The letter may be forwarded to the IRB/IEC at the discretion of the investigator.

7.2 Assessing and Recording Adverse Events

An adverse event is defined as any untoward medical occurrence in a patient or clinical investigation subject administered a pharmaceutical product and which does not necessarily have to have a causal relationship with this treatment. An adverse event can therefore be any unfavourable and unintended sign (including an abnormal laboratory finding, for example), symptom, or disease temporally associated with the use of a medicinal product or protocol-specified procedure, whether or not considered related to the medicinal product or protocol-specified procedure. Any worsening (i.e., any clinically significant adverse change in frequency and/or intensity) of a preexisting condition that is temporally associated with the use of the Sponsor's product, is also an adverse event.

Changes resulting from normal growth and development that do not vary significantly in frequency or severity from expected levels are not to be considered adverse events. Examples of this may include, but are not limited to, teething, typical crying in infants and children and onset of menses or menopause occurring at a physiologically appropriate time.

Sponsor's product includes any pharmaceutical product, biological product, device, diagnostic agent or protocol-specified procedure, whether investigational (including placebo or active comparator medication) or marketed, manufactured by, licensed by, provided by or distributed by the Sponsor for human use.

Adverse events may occur during clinical trials, or as prescribed in clinical practice, from overdose (whether accidental or intentional), from abuse and from withdrawal.

For randomized subjects only, all adverse events that occur after the consent form is signed but before treatment allocation/randomization must be reported by investigator if they are the result of a protocol-specified intervention, including but not limited to washout or discontinuation of usual therapy, diet, placebo treatment or a procedure. From the time of treatment allocation/randomization through 19 days following cessation of treatment, (5 days after Day 28) all adverse events must be reported by the investigator. Such events will be recorded at each examination on the Adverse Event case report forms/worksheets. The reporting timeframe for adverse events meeting any serious criteria is described in section 7.2.3.1. The investigator will make every attempt to follow all subjects with non-serious adverse events for outcome.

Electronic reporting procedures can be found in the Electronic Data Capture (EDC) data entry guidelines. Paper reporting procedures can be found in the Investigator Trial File Binder (or equivalent).

7.2.1 Definition of an Overdose for This Protocol and Reporting of Overdose to the Sponsor

The subject has taken (accidentally or intentionally) any drug administered as part of the protocol and exceeding the dose as prescribed by the protocol. It is up to the investigator or the reporting physician to decide whether a dose is to be considered an overdose, in consultation with the Sponsor.

If an adverse event(s) is associated with (“results from”) the overdose of Sponsor's product or vaccine, the adverse event(s) is reported as a serious adverse event, even if no other seriousness criteria are met.

If a dose of Sponsor's product or vaccine meeting the protocol definition of overdose is taken without any associated clinical symptoms or abnormal laboratory results, the overdose is reported as a non-serious Event of Clinical Interest (ECI), using the terminology “accidental or intentional overdose without adverse effect.”

All reports of overdose with and without an adverse event must be reported by the investigator within 24 hours to the Sponsor either by electronic media or paper. Electronic reporting procedures can be found in the EDC data entry guidelines. Paper reporting procedures can be found in the Investigator Trial File Binder (or equivalent).

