1.0 TRIAL SUMMARY

Abbreviated Title	Multiple ascending dose study of MK-5160 in subjects with Type 1 and Type 2 diabetes mellitus
Sponsor Product Identifiers	MK-5160
Trial Phase	Phase 1
Clinical Indication	Diabetes mellitus
Trial Type	Interventional
Type of control	Placebo and active control without placebo
Route of administration	Subcutaneous
Trial Blinding	Double-blind
Treatment Groups	Part 1 (T1DM): MK-5160 16 nmol/kg or glargine 0.4 U/kg MK-5160 32 nmol/kg or glargine 0.4 U/kg MK-5160 </= 64 nmol/kg or glargine 0.4 U/kg Part 2 (T2DM): MK-5160 16 nmol/kg or glargine 0.6 U/kg MK-5160 32 nmol/kg or glargine 0.6 U/kg MK-5160 </= 64 nmol/kg or glargine 0.6 U/kg
Number of trial subjects	Approximately 48 subjects will be enrolled.
Estimated duration of trial	The Sponsor estimates that the trial will require approximately 8 months from the time the first subject signs the informed consent until the last subject's last study-related phone call or visit.
Duration of Participation	Each subject will participate in the trial for approximately 6-8 weeks from the time the subject signs the Informed Consent Form (ICF) through the final contact. After a washout phase of 4 days each subject will be receiving assigned treatment for approximately 2 weeks. After the end of treatment each subject will be followed for 19 days.
Randomization Ratio	3:1 (MK-5160/glargine)

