Blood for Serum Anti-glargine (Insulin) Antibody/ Immunogenicity Assay						X													X		X
Blood for Serum Anti-MK-5160 Antibody/Immunogenicity Assay						X												X		X	
Pharmacokinetics Evaluations																					
Blood for Plasma MK-5160 and/or Metabolites assay or Glargine ^{k,l}						X	X	X	X	X	X	X	X	X	X	X	X	X	X	X	
Pharmacodynamic Evaluations																					
IV infusion of insulin						X											X				
IV infusion of dextrose						X											X				
Euglycemic Clamp/Infusion of Glucose ^m							X											X			
Blood for Glucose Bedside Analysis ^o							X										X				
Fingerstick Glucose Testing ^p		X	X	X	X		X	X	X	X	X	X	X	X	X	X	X	X	X		
Continuous Glucose Monitoring		X				X											X				

- a. All subjects will participate in only 1 Panel.
- b. Screening should be done within 30 days of Day 1.
- c. Weight will be obtained with the subjects shoes off, jacket or coat removed, with a single calibrated scale. Weight obtained at baseline (Day -1) will be used for determining amount of drug to be administered.
- d. All ECGs will be obtained in triplicate at least 1-2 minutes apart daily around the same time on non-clamp days (predose). On Day -1, ECGs will be obtained. The mean of these measurements will be used as the baseline. During the clamp procedure (see Clamp Flow Chart) ECG measurements will be taken in triplicate at predose, 60 min (1.0 hr), 180 min (3.0 hr), 360 min (6.0 hr), 9.0 hr, 12.0 hr, 18.0 hr, 24.0 hr, 30.0 hr and 36.0 hr. Measurements will also be collected at Post clamp.
- e. At screening, the mean of 3 measurements taken within a 10-minute period (all 3 sets completed within 10 minutes) will be used to assess for subject eligibility. This may be repeated on a second screening day at the discretion of the study investigator. On Day 1, HR and BP will be triplicate measurements obtained at least 1-2 minutes apart within approximately 60 minutes prior to dosing MK-5160/glargine. The mean of these measurements will be used as the baseline. On the day of clamp procedures, post-dose Vital Sign assessments will be done at 30 min (0.5h), 60 min (1h), 180 min (3.0 hr), 360 min (6 hr), 9.0 hr, 12.0 hr, 18.0 hr, 24.0 hr, 30 hr, and 36 hr.
- f. Injection site local tolerability assessment will be recorded as an AE if any reactions are identified.
- g. Adverse experiences (including serious adverse events) will be reported from the signing of informed consent through 33 days (5 days from Day 28) following cessation of treatment.

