7.1.5.2 Treatment Period Visit

Subcutaneous MK-5160 or glargine will be administered as a daily injection from Day 1 to Day 12.

Exogenous glucose will also be infused concurrently with adjustments as needed to maintain a stable glucose concentration predefined by the subject's baseline fasting glucose during the clamp procedure and longer if necessary. Details of this euglycemic clamp technique are outlined in the Study Operations Manual.

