7.1.5.3 Post-Trial

Subjects will be required to return to clinic approximately 16 days (+/ 3 days) after the last dose of trial drug for the post-trial visit. If the post-trial visit occurs less than 16 days after the last dose of trial drug, a subsequent follow-up phone call should be made at 16 days post the last dose of trial drug to determine if any adverse events have occurred since the post-trial

clinic visit. Subjects will be required to return to clinic approximately 16 days (+/- 3 days) post final dose (Day 28) for collection of additional anti-drug antibodies (ADA) and anti-insulin antibodies (AIA) samples.

If a subject has a positive titer at the 28 day follow-up visit, an additional sample will be drawn approximately 56 days (+/- 5 days) after the completion of dosing. At the same time, a fasting plasma glucose sample will be drawn from the subject and an evaluation of possible signs and symptoms of hyperglycemia will be conducted. If medically required the subject will be referred to an endocrinologist for further treatment.

Additional follow-ups will be conducted in intervals of approximately 3 months (+/- 5 days) in subjects with detectable ADAs/AIAs until one of the following occurs:

- a) subject no longer has detectable ADAs/AIAs,
- b) ADAs/AIAs are persistent and stable (titers within 2 to 3-fold of each other) on 3 consecutive checks at 3 month intervals,
- c) return to baseline levels (i.e., within 2 to 3-fold of predose)

An additional fasting plasma glucose sample will be drawn at each time subjects return for ADA/AIA follow-up, and an evaluation of possible signs and symptoms of hyperglycemia will be conducted. Subjects will be referred to an endocrinologist if medically required.

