8.4 Analysis Endpoints

Primary:

Safety

The primary safety endpoints in this study will include all types of adverse experiences, in addition to laboratory safety assessments, ECGs, and vital signs.

Pharmacodynamics

The primary pharmacodynamic variable in this study is the glucose infusion rate (GIR) required to maintain plasma glucose at each subjects' individual clamp target, following administration of MK-5160 or glargine. To assess the primary hypothesis, individual maximal GIR (GIRmax) values at steady state (Day 12) will be used. Prior to obtaining the maximal GIR values, data will be smoothed (LOESS) to minimize variability and the potential impact of transient outliers influencing the estimation. The default smoothing function in SAS PROC LOESS, which selects an optimal smoothing parameter based on minimizing a bias corrected AIC criterion, will be used to fit an optimal smoothing function for each subject.

Additional clamp endpoints that may be analyzed in a similar fashion as above include GIR AUC endpoints over the entire clamp timeframe (0-24 hours) as well as various subfractions of interest (e.g. 0-12, 12-24 hours and 24-end for the Day 12 clamp), though these would be based on raw data and not LOESS smoothed.

Secondary:

Pharmacokinetics

The pharmacokinetic variables of interest include Cmax, Css, Steady State AUC0-24hr, CL, Tmax and t1/2 of MK-5160 after SC administration. Similar endpoints for glargine may also be of interest, as appropriate.

Exploratory:

Pharmacodynamics

The exploratory pharmacodynamic endpoints in this study include FFA, glycerol, triglycerides, β -hydroxybutyrate, glucagon and fasting morning glucose levels, following SC administration of MK-5160 or glargine. Baseline is the Day 1 Predose value.

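### Visits that look for hyperglycemia in antibody-positive subjects all fall after required reporting of non-serious AEs has ended, and Section 8 prespecifies no antibody summary

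*Combined protocol and SAP*

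**What the plan says.** **Dosing.** Section 7.1.5.2: "Subcutaneous MK-5160 or glargine will be administered as a daily injection from Day 1 to Day 12".

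**AE reporting.** Section 7.2 sets this duty on investigators: "From the time of treatment allocation/randomization through 19 days following cessation of treatment, (5 days after Day 28) all adverse events must be reported by" [final words omitted]. Footnote g of the overall flow chart in Section 6.0 gives a different period: "through 33 days (5 days from Day 28) following cessation of treatment". Section 7.2.3.1 uses the same period as Section 7.2 for serious events. After that it requires only serious events judged related to the product to be reported. Section 7.2.3.2 closes the window for events of clinical interest 14 days after treatment ends.

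**Antibody follow-up.** Section 7.1.5.3 provides that, after a positive titer at the Day 28 visit, "an additional sample will be drawn approximately 56 days (+/- 5 days) after the completion of dosing", with a fasting glucose and a check for hyperglycemia at the same visit. Further visits follow about every 3 months while antibodies are detectable, until one of three stopping conditions is met. Also: "An additional fasting plasma glucose sample will be drawn at each time subjects return for ADA/AIA follow-up". The section gives no instruction on recording AEs at these visits.

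**What counts as an AE.** Appendix 12.6 classes a high glucose with symptoms as a clinical AE of hyperglycemia.

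**Analysis.** Section 4.2.3.1, headed as safety endpoints, says that MK-5160 could lead to antibody formation and that drug-induced positives will be tested for neutralizing activity. Section 8.4 states: "The primary safety endpoints in this study will include all types of adverse experiences, in addition to laboratory safety assessments, ECGs, and vital signs". Antibodies do not appear in Section 8 or among the laboratory tests in Table 5.

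**The concern.** Safety is the first primary objective. The protocol schedules visits to look for a specific problem in antibody-positive subjects and defines the symptomatic form of that problem as an AE. Yet the period in which AEs must be reported appears to end before any of those visits takes place.

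Two things are at stake. A non-serious hyperglycemia event that begins after the window and is found at an antibody visit may never reach the safety database, because nothing requires it to. And the antibody results, with the glucose values collected beside them, have no planned place in the safety results by treatment. Panels are small (6 subjects on MK-5160 and 2 on glargine), so a single event that is not captured can change the picture for a panel.

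**Working it through.** The check is study-day arithmetic.

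**Inputs**
- Last dose: Day 12 (7.1.5.2).
- AE reporting: 19 days after cessation, equated with 5 days after Day 28 (7.2, 7.2.3.1); 33 days after cessation, equated with 5 days from Day 28 (footnote g).
- First antibody follow-up: 56 days after dosing, plus or minus 5 (7.1.5.3).
- Later visits: every 3 months, taken here as 91 days (assumption).

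**End of AE reporting**
- Reading A, 19 days after the last dose: 12 + 19 = Day 31.
- Reading B, 5 days after Day 28: 28 + 5 = Day 33.
- Reading C, footnote g taken literally: 12 + 33 = Day 45.

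Section 7.2 treats A and B as the same day, but they differ by 2 days. Counting 19 days from the Day 14 discharge would give Day 33, but Day 14 is not the end of treatment. In footnote g, the bracket (Day 33) contradicts the words around it (Day 45).

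**First antibody visit:** 12 + 56 = Day 68, window Day 63 to Day 73.

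**Days from end of AE reporting to that visit**

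| AE reporting ends | Earliest (Day 63) | Nominal (Day 68) | Latest (Day 73) |
|---|---|---|---|
| Day 31 | 32 | 37 | 42 |
| Day 33 | 30 | 35 | 40 |
| Day 45 | 18 | 23 | 28 |

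The gap is at least 18 days on every reading, so no antibody follow-up visit falls inside the window.

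**Later visits:** 68 + 91 = Day 159, then Day 250 and Day 341. The stopping condition of three stable consecutive checks is met at Day 250 if the Day 68 check counts as the first (68 + 2 × 91), or at Day 341 if it does not (68 + 3 × 91). The other two conditions can end follow-up sooner.

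**Does another clause close the gap?**
- Serious events: only those judged related are reportable after the window.
- Events of clinical interest: 12 + 14 = Day 26, earlier still, and hyperglycemia is not on that list.
- Follow-up of non-serious AEs to outcome (7.2) concerns subjects who already have such an event. It does not clearly reach a new onset after the window.

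**Antibody data without a planned summary.** Section 12.3 plans 3 samples for each of 2 assays at 6 mL: 3 × 2 × 6 = 36 mL per subject, and 3 × 2 × 48 = 288 samples if 48 subjects complete the schedule. The marked redactions in Section 8 sit in the power text, so they do not explain the absence of antibodies from the endpoints and methods.

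**The case against.** A reader might infer that late antibody-related harm is neither reported nor analysed. The text does not go that far. Section 7.2 sets a minimum and does not bar later recording. An AE that is recorded would enter the descriptive summary. Section 8.6 lets selected laboratory parameters be summarized where judged clinically appropriate, and glucose is a Table 5 test. Related serious events remain reportable at any time. What stands is narrower: reporting is not required, and no antibody summary is prespecified.

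A reader might also infer that the trial could report no antibody harm while holding data that show it. That is not demonstrated. The text after the statement on antibody formation in Section 4.2.3.1 is redacted, so the sponsor's view of the consequence is not visible. By Day 68 subjects have been off study drug for 56 days and were to restart home insulin regimens after the final clamp. All have diabetes, with HbA1c up to 10% allowed at entry, so symptomatic hyperglycemia has many background causes. A count of late events could not by itself separate these from an antibody effect. That argues for a listing beside antibody status and glucose; it does not argue for leaving the events uncaptured.

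Antibodies are not absent from the safety plan either: Section 4.2.3.1 treats them under safety endpoints, and the flow chart schedules them. The disagreement is between that section and Section 8.4, and is largely one of missing detail.

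Section 1.0 says "After the end of treatment each subject will be followed for 19 days" and gives 6 to 8 weeks of participation, whereas up to 30 days of screening plus 68 days is 98 days, or 14 weeks. Because the later visits depend on a positive titer, this is a matter of summary wording and carries little weight.

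**Conclusion.** The point holds as a gap in required safety capture. Required reporting of non-serious AEs ends 18 to 42 days before the first visit at which antibody-positive subjects are checked for hyperglycemia, whichever of the three stated end dates applies. Section 7.2 taken alone gives 30 to 42 days. The protocol therefore schedules a search for an event it defines as an AE without requiring the finding to be reported. Subjects are still evaluated and referred where needed; the defect is in the data, not in their care.

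The missing antibody summary is a secondary matter of SAP detail.

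The conclusion rests on Day 12 as the end of treatment and on the plain wording of the windows. It needs no assumption about how often antibodies occur. The documents give no such rate, so the number of subjects affected cannot be stated. Follow-up under Section 7.1.5.3 applies to any subject with a positive titer, among the 36 planned on MK-5160 (6 panels × 6) and the 12 on glargine (6 × 2).

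**What to change.** 1. Reconcile the AE end dates in Sections 7.2 and 7.2.3.1 and in flow chart footnote g (Day 31, 33 or 45), so that one date is stated throughout.
2. In Section 7.2, require hyperglycemia findings at the Section 7.1.5.3 visits to be recorded as AEs, classified under Appendix 12.6, through the subject's last antibody visit. Apply this to every antibody-positive subject, on MK-5160 or glargine. Keep it to hyperglycemia, which is what those visits evaluate.
3. Present these late events in a separate listing with the paired fasting glucose and antibody status. Do not pool them into the main AE incidence: only antibody-positive subjects are followed that long, and pooling would compare groups with unequal observation time.
4. As supporting detail, add to Sections 8.4 and 8.6 a descriptive ADA/AIA summary relative to the predose sample, with neutralizing status, by treatment and part. The predose reference fits the third stopping condition in Section 7.1.5.3, which already compares titers with predose.

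**Cost.** Protocol and SAP wording, one table and one listing. The visits, samples, glucose measurements and symptom checks are already planned. AE forms stay open longer for antibody-positive subjects, and a supplementary safety listing may be needed after the main report.
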